6.1 Eligibility criteria

Subjects participating in the study must be diagnosed with Heart Failure according to the ESC Guidelines for the diagnosis and treatment of acute and chronic heart failure.

[2021 ESC Guidelines for the diagnosis and treatment of acute and chronic heart failure](#)
(McDonagh et al 2021)

Inclusion criteria

- Heart failure (HF) patients with NYHA Functional Class \geq II (according to 2021 EU guidelines).
- Patients who have suffered an acute decompensation of HF (first and recurrent) in the 30 days prior to enrollment in the study.
An acute decompensation of HF is defined as a new episode of symptoms and signs that requires intravenous decongestive treatment or an increase in oral diuretics, either on an outpatient basis (e.g., hospitalization for HF during the day or at home) or in the emergency service or that requires an unplanned hospital admission.
- NT-pro BNP \geq 300 pg/mL or BNP \geq 100 pg/mL at the time of inclusion in the study for patients without ongoing atrial fibrillation/flutter. If there is ongoing atrial fibrillation/flutter, NT-pro BNP should be \geq 600 pg/mL
- Patients must have had an echocardiogram during their HF hospitalization or the previous 12 months.
- Prior to the initiation of any procedures, the hospital will ensure that an informed consent document completed by the patient is obtained.
- All patients will be eligible regardless of the level of LVEF: HFrEF, HFmrEF, and HFpEF.

Exclusion criteria

- Oncology patients with metastasis or with chemotherapy treatment ongoing
- Patients participating in other studies or trials.
- Patients not willing to participate.
- Patients over 150 kg
- Patients who do not use Catalan, Spanish, English, Portuguese, Italian, Dutch, German, Swedish, Hungarian, Romanian, or French.
- Patients without a mobile phone
- Patients without internet connection
- Patients with moderate or severe cognitive impairment without a competent caregiver.
- Patients with severe psychiatric illness.
- Patients with planned cardiac surgery.
- Patients with planned heart transplant or LVAD implant.

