5.2 Primary and secondary endpoints

Primary endpoints

- Creation of a labeled and diverse dataset from a multicenter perspective. The dataset will contain the following data:
 - Physiological parameters: heart rate, calories consumed, steps count, physical activity, oxygen saturation, heart rate variability measurements, stress levels, sleep tracking data, systolic and diastolic blood pressure, weight, BMI
 - Socio-demographic data: sex, age, ethnic group, employment, level of education, number of people living with the patient, caretaker.
 - Risk factors: comorbidities, diabetes, hypertension, smoking, alcohol consumption, heart disease history
 - Medication tracking: lipid-lowering medication, PCSK9 inhibitors, beta-blockers, anticoagulation agents, ACE inhibitors, anti-arrhythmic drugs, anti-inflammatory drugs, aldosterone antagonists, angiotensin receptor/neprilysin inhibitor, other diuretics
 - Symptomatology questionnaire for patients
 - NYHA-class
 - Left Ventricular Ejection Fraction (LVEF)
 - Clinical interventions: hospital readmission, mortality, UCI visits
 - Health questionnaire answers: self-care, quality of life
 - Classified alarms with their respective timestamp and annotation by the medical professionals
 - Measurement ranges for each personalized alarm and their changes

- Implementation of ML models to improve the current alarm-based system using the dataset created. The models should:
 - Provide a relevance level for each new alarm by reducing the number of irrelevant alarms and thus fostering personalized follow-up.
 - Be robust across different new hospitals and reliable and fair across different target populations, considering the diverse sociodemographic data that will be available in the dataset.

Secondary endpoints

- Development and implementation of ML event prediction algorithms that will add new self-generated alarms to the system. These alarms should forecast:
 - Untracked hospital interventions, such as UCI visits or hospital readmissions.
 - Changes of medication with their particular estimated dose.
 - Clinical events, such as mortality.
- Assessment of patient and medical professional's satisfaction with and usability of the digital platform at the end of the study by means of the "System Usability Scale" (SUS) (Brooke, 1986) and the "Post-Study Usability Questionnaire" (PSSUQ).

6 Subjects/population(s)

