 - Patients will answer first the European Heart Failure Self-Care Behaviour Scale (EHFScB scale), the Quality-of-life SF-12 and the Mobile Device Proficiency questionnaires through the app.
- **Day 0 until the end of the study:** Registration of measurements and questionnaires: Patients will be notified through the app whenever they need to register a measurement or answer a health questionnaire. Weight, blood pressure (systolic and diastolic) and oxygen saturation (through the pulse oximeter) will be registered daily. Times for each registration are specified below. Smartwatch device measurements are automatically registered once synchronized with the app. Health questionnaires will be delivered periodically through the app to the patient. Specifically, the symptomatology questionnaire will be delivered twice a week (on Mondays and Thursdays) and the self-care and quality-of-life questionnaires will be answered periodically (specified below).
- **Day 0 until the end of the study:** Medical professionals will follow up on patient's adherence to the study by checking their measurements and health questionnaire answers through the platform. Clinicians will make a control call in case of missing data.
- **Day 0 until the end of the study:** Medical professionals are required to annotate each alarm whenever they receive it and check its relevance. If they are unable to evaluate it at the time of appearance, they are allowed to do it later. However, we strongly recommend annotating the alarms, if there are

any, on a daily basis. Annotations will include adding information about the relevance of an alarm by assessing the health status of the patient.

- **Day 0 until the end of the study:** Medical professionals must report every hospital readmission, mortality, emergency department visit or non-fatal HF decompensation of each patient whenever it happens through the platform. If they are unable to register the event at the moment, events can be registered later on through the platform with their corresponding date/s and duration.
- **Day 0 until the end of the study:** Medical professionals are required to report every medication change through the platform, both due to an alarm-derived decision or derived from a clinical evaluation.
- **Day 7 to 10:** First follow-up visit: Medical professionals will cite the patients for in-person follow-up visits.

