| | Diabetes | | | | |
| | Hypertension | | | | |
| | Smoking | | | | |
| | Alcohol use | | | | |
| | Heart disease history | | | | |
| | NYHA-class | Scale from 1 to 4 | Initial data and if modified | | At the time of inclusion. Medical professionals through the platform |
| | Level of Ejection Fraction (LVEF) | Percent (%) | Initial data and if modified | | At the time of inclusion. Medical professionals through the platform |
| Medication | Lipid lowering medication | Milligrams per day (mg/day) or grams per day (g/day) | Initial data and if modified | Medical professionals through the platform | |
| | PCSK9 inhibitors | | | | |
| | Beta blockers | | | | |
| | Anticoagulation agents | | | | |
| | ACE inhibitors / Angiotensin receptor-neprilysin inhibitor | | | | |
| | Anti-arrhythmic drugs | | | | |
| | Anti-inflammatory drugs | | | | |
| | Aldosterone antagonists | | | | |
| | Antidiabetic | | | | |

| | | | | | |
|-----------------|---|------------------|---|---|--|
| | agents Vericiguat Diuretics SGLT2 inhibitor (Dapaglifrocina/e mpagliflocina) Ivabradina | | | | |
| Symptoms | Chest pain | Yes or not | 2 times per week. On Mondays and Thursdays | | Patients through app questionnaire |
| | Shortness of breath | | | | |
| | Oedema | | | | |
| Clinical events | Hospital readmission | Number and dates | At occurrence | Medical professionals through the platform | |
| | Non-fatal HF event | | | | |
| | Emergency department visits | | | | |
| | Death | Yes/No and date | | | |
| Questionnaire | European Heart Failure Self-Care Behaviour Scale (EHFScB scale) | From 0 to 100 | 4-5 times: when included in the study, 7 days after discharge, 1 month, 3 months, 6 months | Patients through app questionnaire | |
| | Minnesota living with heart failure questionnaire (MLHF) | | | | |
| | Mobile Device Proficiency Questionnaire | From 8 to 40 | 2 times: when included in the study and at the end of the study | | |
| | Morinsky-Green medication adherence 4-item questionnaire | From 0 to 4 | 4 times: when included in the study and once every month | | |

The questionnaires delivered to the patients are specified below and added in the Annex 1:

- Minnesota Living with Heart Failure Questionnaire (MLHF) (Bilbao et al., 2016)
- European Heart Failure Self-care Behaviour Scale (EHFScB scale) (Jaarsma et al., 2009)

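### Alarm-prompted medication changes, and possibly HF events, become forecast labels, and no data field separates them from the rest

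*Combined protocol and SAP*

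**What the plan says.** **Who does what.** Section 4.1 describes an alarm that fires when a measurement leaves a preset range. Under 8.2.1, "Medical professionals are required to annotate each alarm whenever they receive it and check its relevance". The same role "must report every hospital readmission, mortality, emergency department visit or non-fatal HF decompensation of each patient" and reports every medication change, "both due to an alarm-derived decision or derived from a clinical evaluation". No adjudication of events and no blinding to alarms is described.

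**What is forecast.** The secondary endpoints (5.2 and the synopsis) name three targets:
- hospital interventions ("Untracked hospital interventions, such as UCI visits or hospital readmissions"; the synopsis names emergency department visits instead of UCI visits)
- medication changes, with an estimated dose
- clinical events, with mortality as the only example

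**How an HF event is defined.** Section 6.1 gives the only definition, as part of an inclusion criterion. It has two limbs. The first is clinical: symptoms and signs must appear as a fresh episode. The second concerns treatment or setting: the episode "requires intravenous decongestive treatment or an increase in oral diuretics, either on an outpatient basis", or is treated in an emergency department, or leads to an unplanned admission. Section 8.2.1 then asks for non-fatal HF decompensations, and Table 1 in 8.2.3 stores "Non-fatal HF event" as number and dates. Neither place restates the 6.1 definition or refers to it.

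**How performance is judged.** Section 7 plans k-fold cross-validation, a held-out portion of the data, the C statistic (area under the ROC curve) and a calibration plot.

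**The concern.** A forecast should be judged against outcomes that do not arise from the predictor itself. Here the alarm rule reads the measurements that will feed the forecast model, a clinician sees the alarm and may act, and the same professional role records the act as a label. A model that does no more than reproduce the range rule would then appear to anticipate decisions that the rule set in motion. At stake are the forecasting claims (a secondary endpoint) and the labelled dataset (a primary endpoint). If the reason for a decision is not captured when it is entered, it is hard to recover later.

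**Working it through.** The plan gives no event rate, alarm rate or performance target, so there is no figure to reproduce. Steps 1 to 3 compare sections. Steps 4 to 6 are illustrations in which every input is assumed.

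**Step 1: medication changes.** Section 5.2 makes them a target. Section 8.2.1 pools alarm-derived changes with clinically derived ones. Table 1 records each drug at baseline and when modified, with no field for the reason. The alarm annotation concerns the alarm's relevance, not whether a decision followed from it. Some labels are therefore products of the alarm rule and cannot be picked out.

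**Step 2: HF events.** Two links are needed. First, the 6.1 definition must be carried over to follow-up, which is plausible because no other is given and 8.2.1 uses the word decompensation. Second, non-fatal HF events must be a target. Section 5.2 does not name them, but its clinical-events target is open-ended, and Table 1 uses that class name for readmission, non-fatal HF event, emergency visit and death. If both links hold, an alarm-prompted oral diuretic increase in a patient judged to have a new episode is recorded as an HF event as well as a medication change.

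**Step 3: planned checks.** Cross-validation folds and the hold-out come from the same records and carry the same labels, so neither can reveal the problem.

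**Step 4: upper-bound illustration for HF events.** Assume 0.3 events per patient in 6 months arising independently of alarms, of which the model catches 30%. Add r alarm-prompted labels per patient, all spurious and all caught.
- Alarm-made share = r / (0.3 + r)
- Apparent sensitivity = (0.3 × 0.30 + r × 1.0) / (0.3 + r)

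| r | Alarm-made share | Apparent sensitivity |
|---|---|---|
| 0.1 | 0.1/0.4 = 25% | 0.19/0.4 = 48% |
| 0.3 | 0.3/0.6 = 50% | 0.39/0.6 = 65% |
| 1.0 | 1.0/1.3 = 77% | 1.09/1.3 = 84% |

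**Step 5: relaxing those assumptions at r = 0.3.** If half of the alarm-prompted labels are genuine episodes, true sensitivity is (0.09 + 0.15) / 0.45 = 53% against an apparent 65%. The gap is 12 points instead of 35. If the model catches alarm-prompted labels at only 30%, apparent sensitivity is (0.09 + 0.09) / 0.6 = 30%, and there is no inflation.

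**Step 6: an alarm with no skill.** Per risk window, let p be the true event probability, f the alarm probability (independent of the event), and q the share of alarms without a true event that lead to a recorded one. Take p = 5%, f = 30%, q = 10%.
- Recorded rate = p + (1 − p)fq = 0.05 + 0.0285 = 7.85%
- Alarm-made share = 0.0285 / 0.0785 = 36%
- Positive predictive value = p + (1 − p)q = 14.5%, against 5.0% when q = 0
- Sensitivity = 0.30 × 0.145 / 0.0785 = 0.554
- Specificity = 0.95 × 0.70 / 0.9215 = 0.722
- Area under the curve = (0.554 + 0.722) / 2 = 0.638, against 0.500 when q = 0

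Over p = 2% to 10%, f = 10% to 30% and q = 2% to 20%, the area runs from 0.509 to 0.784.

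**The case against.** A reader might infer that any diuretic increase after an alarm is by definition an HF event, so that forecast performance as a whole is circular. The documents do not support that, for four reasons.

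- The 6.1 definition first requires a new episode of symptoms and signs. An increase made only because a reading was out of range does not meet it. If a genuine episode is present, the alarm detected it and did not create it.
- The definition is an eligibility criterion. Its use as an outcome definition is an inference. What the documents show directly is that the follow-up event is undefined.
- Non-fatal HF decompensation is not a named target. For readmission and mortality, acting on an alarm may avert the event, so the bias could go in the opposite direction.
- The figures in step 4 treat every alarm-prompted label as false and always caught. The planned model is not the existing alarm, and step 5 shows that the inflation can shrink to nothing.

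Two further points have weight. Table 1 dates readmissions and emergency visits separately, drug changes are recorded and alarms are timestamped, so some of the separation could be rebuilt by linkage. Section 7 also plans a later randomised trial in other hospitals.

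These points limit the size and reach of the problem but do not remove it. The symptom requirement is judged by professionals who see the alarms, in patients of NYHA class II or above with a recent decompensation. Timing can show that an alarm came first, but not that it prompted the decision. The later trial does not correct performance reported from this study. The medication-change target needs none of the inferences.

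**Conclusion.** The point holds, at moderate severity. It is firmest for medication changes: a named target whose labels pool alarm-derived and other decisions with no means of separating them. For non-fatal HF events it is conditional on the eligibility definition being carried over and on those events being counted among the forecast clinical events. It is not shown for readmission or mortality.

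The size is unknown. The 48%, 65% and 84% are upper-bound illustrations; the area of 0.638 for a no-skill alarm shows only that the mechanism would matter if a tenth of alarms without a true event led to a recorded one. No figure stated in the plan is wrong.

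**What to change.** **Sections 8.2.1 and 8.2.3 (Table 1).** Add to every medication change and every clinical event a field: decision prompted by a platform alarm, yes or no. For each non-fatal HF event, also record whether it involved intravenous treatment, an emergency visit or admission, or an oral diuretic increase only. State whether the 6.1 definition applies to the follow-up event.

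**Section 7.** State that forecast performance for medication changes and clinical events will be reported with and without alarm-prompted labels, that performance claims will rest on labels that were not alarm-prompted, and that HF events will also be shown by type. Say how the restricted analysis treats alarm-prompted labels (excluded, or recoded as non-events).

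Removing all oral-diuretic-only events from the main result is not recommended. It would discard genuine outpatient episodes and still leave alarm-prompted emergency visits and admissions in place.

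**Cost.** Two extra fields and a short addition to section 7. The restricted analysis has fewer events and wider intervals, and it drops genuine episodes that an alarm detected, which is why both versions should be shown. The change concerns recording and analysis only; care is unchanged.

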6.2 Recruitment and screening

For the creation of the dataset, many hospitals have been contacted. Patients will be included in the study based on the eligibility criteria mentioned and must complete the informed consent provided on day 0. Patients will be monitored for 6 months after being included in the study on day 0. Each hospital will decide when to include their patients according to their particular clinical practice (either in the process of discharge planning or during the first follow-up visit, i.e.. 1 or 2 weeks after discharge).

The recruitment period is defined as 6 months. That means patients will be incorporated into the study from its start until the sixth month. The last subject included in the study will then finish the study after one year from the first day of the study (study KICKOFF: first patient - first day).

Medical professionals from each hospital will be in charge of recruiting the participants. The recruitment rate is specific for each hospital, and it may vary depending on the month.

If the recruitment target is not reached for a specific center at the end of the recruitment period (6 months), the latter may be extended until the accorded number of participants recruited is satisfied under the hospital decision.

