For instance, a similar study (Koulaouzidis et al., 2016) with 308 HF patients telemonitored for around 9 months predicted whether patients would undergo hospital readmission during the following day based on the day-to-day physiological measurements of each patient. Performance accuracy was high. However, more specific measures such as the sensitivity were very low, putting patients at a high risk of misclassification.

During model development and training, k-fold cross-validation will be implemented to fine-tune the model parameters and ensure robustness. Additionally, part of the data won't be used during training and validation in order to test model performance on new data never seen by the algorithm. After the implementation of the AI system into the platform, a randomized controlled trial will be carried out in hospitals that didn't participate in the present observational study to externally validate the ML models. In this future study, a quantitative sample size evaluation will be possible by comparing clinical outcomes between the control and study group.

Therefore, the sample size for the present study has been determined qualitatively taking into consideration the reasons mentioned above, that during the 3 first months after HF decompensation is when patients present more harmful events, and the budget available for the project. The plan is to include the maximum number of participants while accomplishing a relevant socio-demographic diversity in the final cohort. We consider that a total of 500 patients will give sufficient data diversity and classified events (alarms + unexpected interventions) to ensure a robust model performance.

Once the algorithms are developed, model performance in terms of accuracy will be evaluated by means of C statistic, the area under the receiver operating characteristic curve, and by creating a calibration plot. Furthermore, we will evaluate the models in terms of fairness and potential bias using metrics such as statistical parity, group fairness, equalized odds, and predictive equality.

8 Conduct

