8.2 Study management, study monitoring, data and sample management

8.2.1 Study management and clinical procedures.

- Recruitment phase: once the CEIm protocol has been approved for each hospital, the assigned medical professionals responsible for the study will be in charge of including patients in the study, following the inclusion criteria. They will explain the study characteristics to the patient and ask if they are willing to be included in the study. The patient will sign the informed consent that includes the acceptance to use active and passive data. Once accepted, the medical professionals will register the user into the platform, fill in all the data required about their socio-demographics and risk factors, and will train the patient on the proper use of the app and devices. The specific calendar for each hospital will depend on its particular involvement and protocol approval date.
- Execution of the study: during the study, patients and medical professionals will evolve as mentioned below.

- **Day 0:** First visit and study enrollment either before or after HF hospital discharge or HF decompensation. This first visit will include,
 - Explanation of the study to the patient and doubt clarification
 - Explanation of the terms and conditions, and signature of the informed consent
 - Medical professionals will register the patient to the HumanITcare platform together with their personal credentials. They will train patients on the proper use of the app and medical devices.
 - Patients will be given a blood pressure monitor, a smartwatch and, a pulse oximeter. Devices will be synchronized with the app (or with the provider's app in some cases). The patient should wear the smartwatch during the entire study period, charging its battery whenever it is about to run out and putting it back on just after it is fully charged.
 - Registration of the following patient variables into the platform by the medical professional:
 - Socio-demographic data: Age, sex, ethnic group, employment, education level, caretaker, number of people living with the patient
 - Risk factors: Comorbidities, diabetes, hypertension, smoking, alcohol consumption, heart disease history
 - Height
 - New York Heart Association (NYHA) Functional Classification
 - Left Ventricular Ejection Fraction (LVEF)
 - Medication use and doses

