- **Day 90 (3 months):** Second follow-up visit: Medical professionals will cite the patients for in-person follow-up visits.
- **Day 180 (6 months):** Last follow-up visit and end of the study: The patient monitoring will finish after 6 months from inclusion to the study (first hospital discharge). Patients should answer the European Heart Failure Self-Care Behaviour Scale (EHFScB scale), the Minnesota Living with Heart Failure questionnaire, the Mobile Device Proficiency Questionnaire, the “System Usability Scale” (SUS) and the “Post-Study Usability Questionnaire” (PSSUQ). Then, they will be required to return the medical devices and medical professionals will change the status of the patient to “finished” on the platform.
Medical professionals will be asked to answer the SUS and PSSUQ questionnaires at the end of the whole study period.
- Medical professionals may cite patients for more in-person visits depending on the specific clinical practice of each center.

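### The dataset has no index decompensation or discharge date, so time since decompensation at enrolment, which may differ between hospitals, is not available to the event-prediction models

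*Combined protocol and SAP*

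**What the plan says.** - **Enrolment time.** Section 6.2 leaves it to the sites: "Each hospital will decide when to include their patients according to their particular clinical practice". The two options given are discharge planning and the first follow-up visit one or two weeks after discharge. Section 8.2.1 describes day 0 as "First visit and study enrollment either before or after HF hospital discharge or HF decompensation".
- **Index episode.** Section 6.1 admits "Patients who have suffered an acute decompensation of HF (first and recurrent) in the 30 days prior to enrollment in the study". The episode need not involve admission; it is enough that it "requires intravenous decongestive treatment or an increase in oral diuretics, either on an outpatient basis".
- **Why timing matters.** In justifying the sample size, Section 7 says that "during the 3 first months after HF decompensation is when patients present more harmful events".
- **Use of the data.** A secondary endpoint in Section 5.2 is "Development and implementation of ML event prediction algorithms that will add new self-generated alarms to the system". These alarms are to forecast readmission and mortality, among other outcomes.
- **What is recorded.** The day-0 list in 8.2.1 holds socio-demographics, risk factors, height, NYHA class, LVEF and medication. Table 1, presented as the complete account of collected data, gives dates for readmission, non-fatal HF event, emergency visit and death, entered as they occur. From day 0 onward, staff "must report every hospital readmission, mortality, emergency department visit or non-fatal HF decompensation of each patient whenever it happens".
- **Clock wording.** Under the day-180 visit, 8.2.1 states: "The patient monitoring will finish after 6 months from inclusion to the study (first hospital discharge". Table 1 times one administration of the self-care and quality-of-life questionnaires at seven days from discharge.

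**The concern.** The plan names time since decompensation as a driver of event frequency, lets that time vary at entry by up to 30 days, and then lists no field from which it can be calculated. Study day is known, but the offset between study day and time since the index episode is not. Two patients on the same study day may stand at different points after their decompensation. Because enrolment time is a site choice, part of the offset may also differ between hospitals.

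The dataset is itself a primary endpoint and the source for the event-prediction models. Sites must already know the date of the episode to apply the 30-day criterion. At stake is a plausible predictor that would be missing from the dataset although it is known at the moment of enrolment.

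**Working it through.** The plan states no figure for this point, so there is none to reproduce. The check has three steps.

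**1. Search of the listed fields.**

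| Place | Index decompensation date | Discharge date |
|---|---|---|
| Dataset lists (synopsis and 5.2) | not listed | not listed |
| Day-0 registration list (8.2.1) | not listed | not listed |
| Table 1, risk factors | heart disease history, no date specified | not listed |
| Table 1, clinical events | dated, but reported from day 0 | not listed for the index stay |
| Table 1, questionnaires | none | implied by one time point, no field |

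The index episode precedes day 0, so event reporting does not capture it. The parenthesis in 8.2.1 that equates inclusion with first hospital discharge does not supply the date either. It conflicts with 6.2 and with the day-0 description, it does not fit patients who were never admitted, and it says nothing about when decompensation occurred.

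**2. Share of monitoring inside the early period.** Inputs: lag L from decompensation to day 0, between 0 and 30 days (6.1); 180 monitored days (8.2.1); the first three months taken as 90 days (assumption). Share = (90 − L)/180.

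| L (days) | Days inside first 90 | Share of 180 |
|---|---|---|
| 0 | 90 | 50% |
| 7 | 83 | 46% |
| 14 | 76 | 42% |
| 30 | 60 | 33% |

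A lag of 0 is an extreme for admitted patients, since enrolment in discharge planning already follows a hospital stay.

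**3. Illustrative effect on risk.** The documents give no event rates after decompensation, so all hazard inputs here are assumptions. Time zero is decompensation and discharge is 7 days later. Enrolment at discharge then covers days 7 to 37, and enrolment 14 days later covers days 21 to 51. With a Weibull cumulative hazard C(t) = −ln(1 − F) × (t/180)^k, where F is the 180-day risk and k the shape:

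ratio = [1 − exp(−(C(37) − C(7)))] / [1 − exp(−(C(51) − C(21)))]

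| k | F | 30-day risk, enrolled at discharge | 30-day risk, enrolled 14 days later | Ratio |
|---|---|---|---|---|
| 1 | 0.3 | 5.8% | 5.8% | 1.00 |
| 1 | 0.5 | 10.9% | 10.9% | 1.00 |
| 0.75 | 0.3 | 7.5% | 6.5% | 1.15 |
| 0.75 | 0.5 | 14.0% | 12.3% | 1.14 |
| 0.5 | 0.3 | 8.7% | 6.6% | 1.33 |
| 0.5 | 0.5 | 16.3% | 12.4% | 1.31 |

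If the hazard is instead raised but constant over the first 90 days, both windows lie wholly inside that period and the ratio is 1.00.

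**The case against.** The best case for the plan is that little may be lost. Section 7 cites a study that predicted next-day readmission from day-to-day physiological measurements; daily vital signs and twice-weekly symptoms may carry much of what time since decompensation would add. In-study decompensations are dated, so after a new episode the clock is known. A separate trial in other hospitals is planned to validate the models. All of this stands and limits the size of the point. It does not put the missing date into the dataset.

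Several stronger readings are tempting and are not supported:

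- *The lag differs systematically between hospitals.* Section 6.2 permits this but does not show it. The lag also includes length of stay, and no distribution by hospital is given.
- *The dates are lost for good.* Section 3.2 says data are stored in coded form, Section 3.3 keeps the link to the medical record for the study physician and collaborators with source access, and 8.2.1 allows late entry of events with their dates. Site staff could retrieve the dates.
- *The models will place patients in the wrong risk period.* This would require study day to stand in for time since decompensation, and Section 7 proposes no such predictor.
- *The risk difference is larger when time is counted from discharge.* The plan's statement about harmful events counts from decompensation, so a ratio on the discharge clock does not measure this gap.
- *The questionnaire time is simply an error for patients never admitted.* Table 1 gives four to five administrations, which may allow that one to be skipped. The text does not say so, and clarification is enough.

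**Conclusion.** The point holds as a minor one. Followed exactly, the plan yields a dataset in which time since the index decompensation is not available from the listed fields, although the plan itself links it to event frequency and the lag may differ between hospitals. It bears on the event-prediction models of the secondary endpoint; no effect on the alarm-relevance models is claimed.

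The loss of predictive performance is unknown. The window shares rest on reading three months as 90 days. The ratio of 1.0 to about 1.3 rests on assumed hazard shapes, assumed 180-day risks of 0.3 and 0.5, and discharge 7 days after decompensation; it illustrates a possible range and does not estimate an effect. A reader might infer that the event-prediction models are invalid without these dates. The documents do not support that, because other listed measurements may carry part of the same information.

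**What to change.** Leave enrolment practice unchanged.

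1. Add four fields to the day-0 list and Table 1: index decompensation date; admitted yes/no; inpatient at day 0 yes/no; discharge date, completed when it occurs and marked not applicable if the patient was never admitted.
2. Define the index date in one way for all patients, because symptom onset, start of treatment and admission can differ and several episodes may fall within 30 days. One option is the date on which treatment of the qualifying episode started, using the most recent episode if there are several.
3. In Section 7, name as candidate predictors for the event-prediction models the days since the most recent decompensation (the index episode at day 0, updated by dated in-study decompensations) and inpatient status at day 0. State that the part of the lag set by enrolment practice stays confounded with hospital where a site uses a single enrolment time.
4. Reconcile the parenthesis on first hospital discharge in 8.2.1 with Section 6.2 and the day-0 description. Reconcile the discharge-based questionnaire time in Table 1 with patients never admitted.

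The cost is slight extra data entry, one analysis paragraph and two wording corrections. Everything is known at day 0 except the discharge date of patients enrolled before discharge. Later retrieval by site staff would also work, but entry at day 0 is simpler and more reliable.
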